#### **14.1.2.3 Exploratory Endpoints**

Exploratory endpoints will include: 1) evaluation of correlative biomarkers of systemic immune response as described below and the evaluation of these data with progression-free and overall survival; 2) evaluation of archival tumor expression of PD-L1 and PD-1 expressing tumor infiltrating lymphocytes; 3) evaluation of archival tumor expression of immune gene expression signature; 4) evaluation of neurologic function as measured by the NANO scale and 5) evaluation of change in tumor growth rate as measured by volumetric analysis.

#### **14.1.3 Hypotheses/Estimation**

Objectives and hypotheses of the study are stated in Section 1.0.

#### **14.1.4 Power and Sample Size**

This study will determine whether nivolumab monotherapy and/or nivolumab plus ipilimumab significantly delays progression among patients with recurrent meningioma based on a primary endpoint of PFS-6 with a planned sample size of 25 patients per cohort. Effective therapy for patients with atypical or anaplastic meningioma who progress after surgery and radiotherapy does not exist. A recent meta-analysis of salvage medical therapies for recurrent WHO grade II/III meningiomas refractory to surgery or radiation therapy revealed a weighted PFS-6 of 26% (95% CI: 19.3-32.7%) and 29% (95% CI: 20.3%, 37.7%) among those with grade I meningiomas that progressed after prior radiation therapy.(20) With a sample size of 25 patients per cohort, our study will have 90% power to detect a PFS-6 increase of 25% (26% vs. 51%) using a one-sided significance level of 0.10 (exact alpha=0.089). At the final stage of analysis, the null hypothesis will be rejected and nivolumab monotherapy or nivolumab plus ipilimumab therapy will be considered worthy of further investigation for patients with atypical/anaplastic meningioma if at least 10 patients are progression-free at the six months timepoint.

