## 1. OBJECTIVES

We hypothesize that inhibition of PD-1 signaling will generate meaningful anti-tumor benefit and will be well tolerated for progressive/recurrent meningioma patients. We propose to initially evaluate Nivolumab in an open-label, phase II study for patients with recurrent atypical or anaplastic meningioma. The study has been amended to include a second cohort (cohort 2) of participants where the combination of nivolumab plus ipilimumab is evaluated following administration of radiation therapy. Enrollment to cohort 2 will commence upon completion of enrollment to the original cohort (cohort 1) of participants treated with nivolumab monotherapy. In addition, the study has been amended to include patients with grade 1 meningioma that have progressed after prior radiation therapy based on the lack of effective therapies for these patients and their decreased outcome.

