### 1.2 Primary Objectives

**1.2.1** To evaluate the anti-tumor activity as measured by progression-free survival at six months (PFS-6) for single-agent nivolumab (cohort 1) or nivolumab plus ipilimumab following radiation therapy among patients with recurrent/progressive grade I, II or III meningioma.

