Effective therapy for meningiomas that recur following radiation therapy has not been identified. In particular, overall outcome for patients with progressive grade II and III meningiomas remains particularly poor with most series reporting 5-year survival rates of 28-61%.(18, 19) A recent meta-analysis of all salvage medical therapies evaluated for patients with atypical and anaplastic meningiomas that recur after surgery and radiation, revealed a weighted average PFS-6 rate of 26% (95% CI: 19.3-32.7%).(20) Similarly, meta-analysis data from the literature evaluating treatment of grade I meningioma patients who progressed after initial radiation therapy report a median PFS-6 of 29% (95% CI: 20.3%, 37.7%) and median overall survival of 7-13 months following administration of salvage therapy.(20) Results of several trials evaluating a wide variety of chemotherapy agents have been disappointing(15) although hydroxyurea has demonstrated modest anti-tumor activity in some series.(21, 22) Targeted therapies that inhibit specific activators of dysregulated cell signaling pathways, such as the epidermal growth factor receptor (EGFR) or platelet derived growth factor receptor (PDGFR) have also proven ineffective in clinical trials to date among non-enriched meningioma patients.(23, 24) In addition, hormonal-based therapies have also proven ineffective.(25, 26) Most recently, therapeutic efforts have utilized anti-angiogenic agents for progressive meningiomas based on the observation that levels of vascular endothelial growth factor (VEGF) and VEGF receptor increase with increasing meningioma grade and provide prognostic significance.(27) Two retrospective series report modest therapeutic benefit associated with bevacizumab, a humanized monoclonal antibody against VEGF, for patients with progressive meningiomas.(28, 29) In addition, a recently reported single arm phase II study of sunitinib, an oral VEGFR tyrosine kinase inhibitor, demonstrated modest anti-tumor activity among patients with recurrent atypical and anaplastic meningiomas.(30) In summary, effective treatment of meningiomas that progress following surgery and radiotherapy have not been defined and patients with such tumors remain a major unmet need in modern day oncology. A recent meta-analysis of all salvage medical therapies evaluated for surgery and radiation refractory, recurrent atypical and anaplastic meningiomas revealed a weighted average PFS-6 rate of 26% (95% CI: 19.3-32.7%) and 29% for those with progressive grade I tumors.(20) The poor PFS-6 rate for progressive grade I meningiomas, which is negligibly better than that of grade II or III tumors, indicates that effective therapies for progressive grade I meningiomas are not available. In addition, a subset of grade I meningiomas may transform to grade II or III at recurrence. Based on these considerations, patients with progressive grade I meningiomas are therefore appropriate to consider for treatment with promising salvage therapies in prospective clinical trials, and other clinical trials are doing so (NCT03279692). The current clinical trial has therefore been amended to include patients with grade I meningiomas that have progressed after prior surgery and

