This document is confidential. Do not disclose or use except as authorized.

demonstrate a high rate of therapeutic benefit with ipilimumab plus nivolumab in patients with melanoma, small cell lung cancer, renal cell carcinoma and melanoma brain metastases, although these studies also demonstrate that combination therapy is accompanied by a higher rate of immune related adverse events. More recent trials incorporating a reduced dosing schedule of anti-CTLA-4 have been associated with a decreased rate of immune related toxicity while preserving therapeutic benefit.

In addition to the above data supporting our hypothesis that anti-PD-1 plus anti-CTLA-4 will lead to durable therapeutic benefit when combined with radiation therapy for patients with recurrent grade I, II or III meningioma, there is ample data to support our expectation that this combination regimen will be safe and associated with a tolerable toxicity profile. Although results of radiation therapy plus immune checkpoint blockade have not been reported for meningioma patients, the safety of anti-PD-1 combined with fractionated radiation therapy has been demonstrated for newly diagnosed glioblastoma patients while the addition of anti-PD-1 and anti-CTLA-4 to stereotactic radiosurgery has been confirmed among patients with brain metastases.

In conclusion, our study data to date for Cohort 1 demonstrates that nivolumab monotherapy is associated with encouraging but limited benefit for patients with recurrent grade II or III meningioma. Given that radiation therapy is a standard of care for these patients, and that growing data demonstrates that radiation therapy can synergize to enhance the therapeutic benefit of immune checkpoint blockade, we plan to amend the current study to add a second cohort who will receive dual anti-CTLA-4 plus anti-PD-1 immune checkpoint blockade combined with radiation therapy. We anticipate that our overall study data, evaluating both efficacy and safety of Cohorts 1 and 2, will provide a substantial basis to guide the further clinical development of immune checkpoint therapy for patients with recurrent/progressive grade I, II and III meningioma.

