## 14.1 Statistical Analysis Plan

This section contains a brief summary of the statistical analyses for this trial. This trial includes allocation of accrual to two experimental treatment arms (nivolumab monotherapy or nivolumab plus ipilimumab). The outcome of each treatment arm will be assessed relative to appropriate historical controls.

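### Cohort 2 is tested against a 26% PFS-6 null from medical salvage, with no radiation benchmark, and the go verdict in Section 14.1.4 omits radiation from the regimen's name

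*Combined protocol and SAP*

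**What the plan says.** Section 14.1.4 sets one null (26%), one alternative (51%), one sample size (25) and one final rule (at least 10 progression-free at six months) for each cohort. Section 14.1.5.1 adds one interim rule for each: continue if at least 3 of the first 10 are progression-free, otherwise stop.

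The null rests on "salvage medical therapies for recurrent WHO grade II/III meningiomas refractory to surgery or radiation therapy revealed a weighted PFS-6 of 26" percent. Section 2.1 describes the same source as "A recent meta-analysis of all salvage medical therapies evaluated for patients with atypical and anaplastic meningiomas that recur after surgery and radiation". For grade I tumors that progressed after radiation, Section 14.1.4 quotes 29% but does not use it in the design. Section 14.1 says: "The outcome of each treatment arm will be assessed relative to appropriate historical controls".

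Cohort 2 gets radiation before the drugs. Section 5.2 allows initial radiation or re-irradiation and starts the drugs 1 to 12 weeks after it ends. Criterion 3.1.9 lets patients enroll during radiotherapy, or after completing it within 12 weeks of starting immunotherapy. Criterion 3.1.1 requires failed radiation for grade I tumors only.

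The verdict in Section 14.1.4 reads: "nivolumab plus ipilimumab therapy will be considered worthy of further investigation for patients with atypical/anaplastic meningioma if at least 10 patients are progression-free". Radiation is not named. Objective 1.2.1 does name it: "nivolumab plus ipilimumab following radiation therapy among patients with recurrent/progressive grade I, II or III meningioma".

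**The concern.** The 26% suits Cohort 1, where a drug is given alone, mostly after radiation has failed. Cohort 2 differs in treatment, because radiation is part of the regimen. It may also differ in population, because grade II or III patients may be having their first course. Section 2.1 calls radiotherapy initially effective in many cases, and Section 2.4 calls it a standard of care. Neither gives a PFS-6 for it.

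A go in Cohort 2 can therefore mean two things. It can mean that radiation followed by the drugs does better than 26%, or that the drugs add something. The trial tests only the first. If the verdict is read as the second, an effect of radiation could be credited to nivolumab plus ipilimumab when the next study is chosen. Section 14 states that no separate SAP will be issued, so no later document is planned that would settle the wording.

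**Working it through.** **Inputs.** n = 25, null 26%, alternative 51%, go at 10 or more, one-sided 0.10 with stated exact alpha 0.089 and power 90% (Section 14.1.4). Continue at 3 or more of 10, with stated stopping chances of 0.5 and 0.048 (Section 14.1.5.1). Grade I rate 29% (Section 14.1.4). The PFS-6 of radiation with inactive drugs is not in the documents, so every value used for it below is an assumption. All 25 patients are taken as evaluable at six months.

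**Step 1. The plan's own figures.** With X binomial(25, p), P(X ≥ 10) is 0.0893 at p = 0.26 and 0.9036 at p = 0.51. Both match the plan. The early-stop chance P(X1 ≤ 2 of 10) is 0.496 and 0.048, which also match.

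**Step 2. Adding the interim.** P(go) = Σ over x = 3 to 10 of P(X1 = x of 10) × P(X2 ≥ 10 − x of 15). At p = 0.26 the terms for x = 3 to 8 are 0.0175 + 0.0270 + 0.0231 + 0.0112 + 0.0031 + 0.0005 = 0.082, and the last two are negligible. At p = 0.51 the sum is 0.880.

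**Step 3. The regimen claim.** If the whole Cohort 2 regimen has a PFS-6 of 26% or less, the chance of a go is at most 0.089 (0.082 with the interim). At the plan's own 29% for grade I it is 0.160 (0.148 with the interim). Control therefore holds against a flat 26%, not against every benchmark that the plan quotes.

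**Step 4. The drug claim.** Here the relevant null is p_R, the PFS-6 with radiation and inactive drugs. Setting P(go) = 0.10 and solving gives p_R = 26.9% with the interim, or 26.5% for the final rule alone. At assumed values:

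| Assumed p_R | P(go), with interim | P(stop at interim) |
|---|---|---|
| 20% | 0.016 | 0.68 |
| 26% | 0.082 | 0.50 |
| 30% | 0.18 | 0.38 |
| 40% | 0.55 | 0.17 |
| 50% | 0.86 | 0.055 |

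Below 26% the rule is conservative for a drug claim. Above about 26.9% it exceeds the nominal 0.10.

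**Step 5. What the smallest go shows.** 10/25 = 40%, with an exact (Clopper-Pearson) 95% CI of 21.1% to 61.3%, ignoring the interim. A radiation-alone rate somewhat above 26% would lie well inside that interval.

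**Step 6. The wording, side by side.** Section 14.1.3 says: "Objectives and hypotheses of the study are stated in Section 1.0". Section 1 contains the general hypothesis "We hypothesize that inhibition of PD-1 signaling will generate meaningful anti-tumor benefit and will be well tolerated", and also the regimen objective 1.2.1. The question and the verdict in Section 14.1.4 name only the drugs. Objectives 1.2.1, 1.3.1 and 1.3.2 and the Trial Summary name radiation as well.

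**Step 7. The clock.** Section 14.1.2.1 counts six months from the start of study therapy. Section 7 (first dose of a study drug), Section 11.1.2 (baseline scan tied to Cycle 1 Day 1) and Section 14.2 (efficacy population defined by a dose of study drug) point to the first drug dose. Section 5.7 includes radiation in study therapy.

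**The case against.** The strongest reply is that the verdict is shorthand. Section 14.1 uses nivolumab plus ipilimumab in parentheses as the name of the arm, Section 5.2 carries that name in its heading and includes radiation, and the objectives and the Trial Summary spell out the full regimen. The evidence for a drug claim is thin. The PD-1 hypothesis in Section 1 leads into the plan to study nivolumab first, and the same paragraph then describes the combination as given after radiation. The statement in Section 2.4 that the data "will provide a substantial basis to guide the further clinical development of immune checkpoint therapy" refers to both cohorts together, and the same section hypothesizes benefit in combination with radiation. A finding that something is worthy of further investigation is also a screening decision, not an attribution of effect. All of this stands, and the arm-label reading is the more likely one. It does not remove the gap: the sentence that defines success leaves out a component that the documents themselves call a standard of care, and nothing explains why a medical-salvage rate is the appropriate control for this arm.

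A second reply is that radiation alone may do no better than 26%. Section 2.4 says its benefit is not durable and that most patients progress. Section 11.2 counts any new lesion as progression, and Section 5.6 dates progression outside the irradiated site from its first appearance. This also stands: the documents do not exclude a low rate. They do not support one with a figure either.

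**Conclusion.** The point holds as a matter of what a Cohort 2 go may conclude. The rule is a valid test of whether radiation followed by nivolumab plus ipilimumab exceeds a flat 26% (alpha 0.089, or 0.082 with the interim). It does not support a conclusion about the drugs unless radiation with inactive drugs gives about 26.9% or less, and the documents neither give nor argue such a rate.

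A reader might infer three stronger things that the documents do not support.

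- That the Cohort 2 error rate is inflated. No radiation rate is given, so size and direction are unknown, and the 0.18 to 0.86 at 30% to 50% are results under assumptions.
- That the plan commits itself to a verdict on the drugs alone. The objectives and the Trial Summary point to the regimen.
- That all Cohort 2 radiation is delivered after enrollment. Criterion 3.1.9 allows it to have begun or ended earlier.

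It would also go too far the other way to say that error for the regimen is controlled without qualification, since at 29% the chance of a go is 0.160 (0.148 with the interim).

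This should be fixed, but it does not invalidate the test.

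**What to change.** In Section 14.1.4:

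1. State the Cohort 2 hypothesis and verdict for radiation followed by nivolumab plus ipilimumab, as in 1.2.1.
2. State that the comparison is with a 26% medical-salvage benchmark.
3. Add: *A positive Cohort 2 result does not attribute benefit to nivolumab plus ipilimumab over radiation.*
4. Report Cohort 2 PFS-6 with an exact 95% CI.

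As a secondary clarification, state in Section 14.1.2.1 that the Cohort 2 six-month clock starts at the first dose of study drug, use the same clock at the interim, and reconcile Section 5.7 with it. A clock starting at radiation should not be offered. The efficacy population requires a drug dose, so patients would have to survive and stay in the study from radiation to that dose in order to be counted. A descriptive split by first radiation versus re-irradiation is optional, and its estimates would be wide.

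The cost is a few sentences and one interval, with no extra patients and no new threshold. The downside is a narrower Cohort 2 conclusion. A verdict on the drugs would cost more: it would need a justified radiation-based null from outside data and a re-derivation of both stages, and a single arm would still not isolate the drug effect.

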## TRIAL SUMMARY

Abbreviated Title	Nivolumab for Progressive/Recurrent Meningioma
Trial Phase	II
Clinical Indication	Progressive/recurrent meningioma
Trial Type	Interventional
Type of control	No treatment control
Route of administration	Intravenous
Trial Blinding	Unblinded, open-label
Treatment	
Cohort 1: Nivolumab monotherapy (240 mg every 2 weeks)
 
NOTE: Participants who have received active study therapy for >/= 6 months will be allowed the option to adjust their Nivolumab dosing schedule from 240 mg once every 2 weeks (-2/+5 days) to 480 mg once every 4 weeks (+/- 1 week).
 
Cohort 2: External Beam RT (IMRT, 3D-CRT, or proton-beam radiation therapy), followed by 4 cycles of Nivolumab (3 mg/kg every 3 weeks) + Ipilimumab (1 mg/kg every 3 weeks), followed by Nivolumab monotherapy (480 mg every 4 weeks). A safety lead-in is included for Cohort 2.

Number of trial subjects	Approximately 25 patients will be enrolled in each cohort
Estimated duration of trial	The Principal Investigator estimates that the trial will require approximately 42 months from the time the first participant of each cohort signs the informed consent until the last participant's last visit.

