#### **14.1.5 Interim Analysis**

##### **14.1.5.1 Monitoring of Efficacy**

One interim analysis will be conducted on each cohort. Each Interim Analysis will occur once 10 patients have been followed for at least six months on that cohort. Accrual will not stop for this interim analysis. If at least 3 out of the first 10 evaluable patients are alive and progression free at 6 months, that cohort will proceed to full accrual. If 2 or fewer of the

CONFIDENTIAL

This document is confidential. Do not disclose or use except as authorized.

first 10 evaluable patients have remained progression free at six months, further accrual will be stopped to that cohort and that cohort will be discontinued. Under this stopping criterion, the chances of stopping a cohort early is 0.5 and 0.048 under the null and alternative respectively. The stopping rule for the interim analysis was designed to optimize for a low type II error.

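### The stated 90% power and exact alpha of 0.089 ignore the mandatory interim stop; the design as written has 88.0% power and alpha 0.082

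*Combined protocol and SAP*

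**What the plan says.** Section 14.1.4 describes one test per cohort "with a planned sample size of 25 patients per cohort". The null PFS-6 rate is 26% and the alternative 51%. It claims that "our study will have 90% power to detect a PFS-6 increase of 25% (26% vs. 51%) using a one-sided significance level of 0.10", with the exact alpha given as 0.089, and rejects the null at the final stage if at least 10 patients are progression-free at six months.

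Section 14.1.5.1 adds one interim analysis per cohort, after 10 patients have at least six months of follow-up. With 3 or more of the first 10 evaluable patients progression-free, the cohort goes to full accrual. With 2 or fewer, "further accrual will be stopped to that cohort and that cohort will be discontinued". It then reports that "the chances of stopping a cohort early is 0.5 and 0.048 under the null and alternative respectively". It gives no overall power or alpha for the two stages combined, and nothing describes the stop as advisory.

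The Trial Summary is looser about the sample size: "Approximately 25 patients will be enrolled in each cohort". Section 14.2 takes all participants who received at least one dose as the efficacy population. Section 14 states that no separate statistical analysis plan will be issued, so these paragraphs are the only statement of the decision rule.

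**The concern.** A binding futility stop removes some paths to success, so it lowers both the power and the type I error of the final test. Section 14.1.4 quotes an alpha, to three decimals and labelled exact, and a power that appear to come from the final test alone. If so, the plan overstates its power, and any alpha quoted beside a positive result would not belong to the procedure used. Section 14.1.5.1 says the interim was chosen to keep the type II error low, yet it never reports the resulting overall type II error.

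A related weakness is that the success criterion is a bare count. It has its stated properties only if exactly 25 patients are analysed, and the plan does not say what happens otherwise.

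**Working it through.** **Inputs.** From Section 14.1.4: n = 25, p0 = 0.26, p1 = 0.51, success if X ≥ 10. From Section 14.1.5.1: n1 = 10, stop if X1 ≤ 2. All probabilities are exact binomial.

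**Step 1: reproduce the plan's figures with one stage.**
- Alpha: P(X ≥ 10 | 25, 0.26) = 0.0893, which is the stated 0.089.
- Power: P(X ≥ 10 | 25, 0.51) = 0.9036, which is the stated 90%.
- A count of 9 would give 0.179 and 0.956; a count of 11 would give 0.039 and 0.816. Of these counts, only 10 in a single stage matches both stated figures.

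**Step 2: reproduce the interim figures.**
- P(X1 ≤ 2 | 10, 0.26) = 0.4958, stated as 0.5.
- P(X1 ≤ 2 | 10, 0.51) = 0.0480, stated as 0.048.

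**Step 3: combine the stages.** With X1 successes among the first 10 and Y among the other 15,

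P(success) = Σ over x = 3 to 10 of P(X1 = x | 10, p) × P(Y ≥ 10 − x | 15, p).

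| x | Y needed | product at p = 0.26 | product at p = 0.51 |
|---|---|---|---|
| 3 | 7 | 0.2563 × 0.0684 = 0.0175 | 0.1080 × 0.7233 = 0.0781 |
| 4 | 6 | 0.1576 × 0.1713 = 0.0270 | 0.1966 × 0.8667 = 0.1704 |
| 5 | 5 | 0.0664 × 0.3469 = 0.0231 | 0.2456 × 0.9494 = 0.2332 |
| 6 | 4 | 0.0195 × 0.5742 = 0.0112 | 0.2130 × 0.9855 = 0.2099 |
| 7 | 3 | 0.0031 | 0.1263 |
| 8 to 10 | 2 or fewer | 0.0005 | 0.0621 |
| **Total** | | **0.0823** | **0.8800** |

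**Step 4: cross-check through the lost paths.** The stop removes the terms x = 0, 1 and 2. At p = 0.51 these are 0.0001 + 0.0028 + 0.0207 = 0.0236, and 0.9036 − 0.0236 = 0.8800. At p = 0.26 they come to 0.0070, and 0.0893 − 0.0070 = 0.0823.

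**Step 5: other numbers analysed (an assumption, since the plan gives no such n).** The same sum, with n − 10 patients in the second stage and the count held at 10:

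| n analysed | alpha, count 10 | power, count 10 | smallest count with alpha ≤ 0.10 | alpha / power at that count |
|---|---|---|---|---|
| 23 | 0.050 | 0.810 | 10 | 0.050 / 0.810 |
| 24 | 0.065 | 0.850 | 10 | 0.065 / 0.850 |
| 25 | 0.082 | 0.880 | 10 | 0.082 / 0.880 |
| 26 | 0.102 | 0.902 | 11 | 0.049 / 0.842 |
| 27 | 0.122 | 0.918 | 11 | 0.063 / 0.873 |
| 28 | 0.145 | 0.929 | 11 | 0.078 / 0.896 |

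Without the interim, 28 patients and a count of 10 give alpha 0.168.

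**The case against.** The strongest reply is that this changes little. Power of 88.0% against a stated 90% is a 2.0-point gap in a small single-arm screening trial tested at one-sided 0.10. The sample size, the count of 10 and the interim rule could all stay as they are. The alpha error is conservative, because 0.082 lies below both 0.089 and 0.10. The plan also prints both early-stopping probabilities, so a reader can bound the power loss at 4.8 points. And 0.089 would be the right alpha to report if the futility stop were non-binding, a common convention.

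Most of this stands as a limit on size. It does not rescue the figures. The plan does not call the stop non-binding; it says the cohort will be discontinued. Continued accrual during the interim makes no difference, because a cohort that fails never reaches the final test.

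A second reply concerns sample-size drift. Section 14.1.4 fixes 25, while the approximate wording comes from the summary. Section 5.2.2 replaces only Cohort 2 lead-in patients who are not evaluable for dose-limiting toxicity, and the plan does not say whether replacements fall inside or on top of the 25. That is fair: the figures for 23 to 28 are conditional and secondary. They show what the fixed count does if n moves, not that it will.

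Timing also matters. Under Section 1, Cohort 2 opens only after Cohort 1 has finished enrolling, and Section 2.4 already describes Cohort 1 outcomes. For Cohort 1 the correction can affect reporting only.

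**Conclusion.** The concern holds. The stated power and exact alpha are single-stage values. The design as written has power 0.880 and one-sided alpha 0.082 for 26% against 51%. The type II error is 12.0%, against 9.6% for the single stage (1 − 0.9036) and the 10% the plan implies. The interim costs 2.4 points of power against the exact single-stage value, or 2.0 against the stated 90%. At exactly 25 patients, type I error control is intact.

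This rests on three assumptions: the first 10 evaluable patients are among the 25 analysed, all 25 have a known six-month status, and the stop is applied as written. If more than 25 are analysed with the count still at 10, alpha goes above 0.10, slightly at 26 (0.102) and clearly at 28 (0.145).

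The text should be corrected, but the shortfall does not undermine the design.

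**What to change.** In Section 14.1.4, replace the power and alpha statement with one that includes the interim: with a stop at 2 or fewer of the first 10, the design has 88% power (26% against 51%) and exact one-sided alpha 0.082. Alternatively, state that the stop is non-binding, amend Section 14.1.5.1 to match, and label 0.089 and 90% as figures that disregard it.

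Add a short table of the success count for each realised number analysed, for example 23 to 28, with exact two-stage alpha and power. State whether replaced lead-in patients count toward the 25.

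If the sponsor wants to keep 90% in a cohort whose interim has not yet been done, stopping at 1 or fewer of 10 gives power 0.901 and alpha 0.088. The price is that the chance of stopping early under the null falls from 0.50 to 0.22. This is optional and is not needed to correct the text.

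The cost is one sentence, a small table and a slightly less favourable stated power. No extra patients are required.

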#### **3.1 Eligibility Criteria**

In order to be eligible for participation in this trial, all participants must meet the following criteria on screening examination:

**3.1.1** Have histologically confirmed WHO grade I, II or III meningioma that is progressive or recurrent. Metastatic meningiomas are allowed. Participants with grade I tumors must have failed radiation therapy.

**3.1.2** Prior therapy:

There is no limit on the number of prior surgeries, radiation therapy, radiosurgery treatments or systemically administered therapeutic agents.

For **Cohort 1**: Patients may have been treated with standard external beam radiation or radiosurgery in any combination, however, an interval of  $\geq$  12 weeks (84 days) must have elapsed from the completion of the radiation therapy to start of study therapy unless there is histopathologic confirmation of recurrent tumor or there is new enhancing tumor outside the radiation field (beyond the high dose region or the 80% isodose line). (See Inclusion Criterion 3.1.9 for RT requirements for Cohort 2 patients.)

In addition, there must be subsequent evidence of tumor progression after completion of radiation therapy (grade I tumors only);

An interval of  $\geq$  28 days and full recovery (no ongoing safety issues) from surgical resection ( $\geq$  7 days from stereotactic biopsy).

For prior systemic agents, participants must be at least 4 weeks (or 5 half-lives, whichever is shorter) from other prior cytotoxic chemotherapy (6 weeks from nitrosoureas) or biologic therapies.

**3.1.3** Participants must have recovered to grade  $\leq$  1 or pretreatment baseline from clinically significant adverse events related to prior therapy (exclusions include but are not limited to alopecia, laboratory values listed per inclusion criteria and lymphopenia);

**3.1.4** Be  $\geq$  18 years of age on day of signing informed consent.

CONFIDENTIAL

This document is confidential. Do not disclose or use except as authorized.

**3.1.5** Have a Karnofsky performance status (KPS)  $\geq 70$  (Appendix A).

**3.1.6** Participants must demonstrate adequate organ and marrow function as defined below (all screening labs to be performed within 14 days of treatment initiation):

- White blood cell (WBC)  $\geq 2000/\text{mm}^3$
- Absolute neutrophil count (ANC)  $\geq 1,000/\text{mm}^3$
- Platelet count  $\geq 100,000/\text{mm}^3$
- Hemoglobin  $\geq 9 \text{ gm/dl}$

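### The 10-of-25 rule pools grades I–III but keeps the grade II/III null of 26% and an atypical/anaplastic verdict, so it cannot support that verdict, and alpha = 0.089 holds only with no grade I patients

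*Combined protocol and SAP*

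**What the plan says.** Section 3.1.1 admits patients who "Have histologically confirmed WHO grade I, II or III meningioma that is progressive or recurrent"; grade I patients must have failed radiation, and no limit is set on their number. Section 1.2 states the primary objective as PFS-6 "among patients with recurrent/progressive grade I, II or III meningioma". Section 14.2 makes all treated participants the efficacy dataset, whatever their grade.

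Section 14.1.4 sets a "planned sample size of 25 patients per cohort" and cites two historical rates from one meta-analysis. For grade II/III the analysis "revealed a weighted PFS-6 of 26% (95% CI: 19.3-32.7"%); the second rate is 29% (95% CI 20.3–37.7%) "among those with grade I meningiomas that progressed after prior radiation therapy". Only the first enters the test, which is powered for an "increase of 25% (26% vs. 51%) using a one-sided significance level of 0.10 (exact alpha=0.089"). A cohort that passes "will be considered worthy of further investigation for patients with atypical/anaplastic meningioma if at least 10 patients are progression-free at the six months timepoint".

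Section 14.1.5.1 adds one interim look per cohort: with 2 or fewer of the first 10 evaluable patients progression-free at six months, the cohort is discontinued. Section 14 states that no separate SAP will be issued, so this text is the operative decision rule.

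**The concern.** Grade I patients were added by amendment (Section 1). Their historical rate was brought into the sample-size paragraph, but the null, the cut-off and the wording of the conclusion remained those of a grade II/III trial. Two consequences follow.

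- **The conclusion names a population other than the one tested.** Grade I patients count toward the 10 successes, yet the verdict is for atypical/anaplastic disease only. No analysis by grade is planned to support it, and the rule gives no verdict for the grade I–III population of the primary objective.
- **The stated error rate is tied to a 26% null.** If grade I patients on an inactive regimen do slightly better, as the cited point estimates suggest, the false-positive rate of the fixed cut-off exceeds the printed one.

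At stake is what a go decision from each 25-patient cohort may be said to show.

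**Working it through.** **Inputs.** n = 25, success at 10 or more, 26% vs 51%, one-sided 0.10, and 26% and 29% as the grade II/III and grade I rates (Section 14.1.4). Continue only with at least 3 of the first 10 (Section 14.1.5.1). The grade I share f is not in the documents, so it is varied from 0 to 100%.

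**Reproducing the plan.** With X ~ Bin(25, p):
- P(X ≥ 10 | 0.26) = 0.0893 and P(X ≥ 10 | 0.51) = 0.904, matching the printed 0.089 and 90%. These are single-stage figures that ignore the interim.
- P(Bin(10, p) ≤ 2) = 0.496 at 26% and 0.048 at 51%, matching the printed 0.5 and 0.048.
- With the interim stop applied as written, P(success) = Σ over k = 3 to 10 of P(Bin(10, p) = k) × P(Bin(15, p) ≥ 10 − k). This gives alpha 0.082 and power 0.880.

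**Mixed cohort, inactive drug.** p0 = 0.26(1 − f) + 0.29f = 0.26 + 0.03f.

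| Grade I share | p0 | Alpha, single stage | Alpha, with interim |
|---|---|---|---|
| 0% | 26.0% | 0.089 | 0.082 |
| 20% | 26.6% | 0.102 | 0.094 |
| 40% | 27.2% | 0.115 | 0.106 |
| 50% | 27.5% | 0.122 | 0.112 |
| 100% | 29.0% | 0.160 | 0.148 |

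Alpha equals 0.10 at p0 = 26.529% (single stage), so f = 0.529/3 = 17.6%. With the interim it does so at p0 = 26.919%, so f = 0.919/3 = 30.6%. An exact sum of unequal binomials, with k grade I patients of 25 in random order, agrees. Single stage gives 0.0989 at 4 of 25 and 0.1014 at 5 of 25; with the interim, 0.0983 at 7 and 0.1007 at 8.

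**Cut-off of 11.** Against 29%, alpha is 0.079 single stage and 0.076 with the interim. Power at 51% falls from 0.904 to 0.816, or from 0.880 to 0.801 with the interim. It follows that 11 or more successes give p below 0.10 for any mix of grades at these point estimates. The 10-of-25 decision and a p-value against the weighted null can disagree only at exactly 10 successes.

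**Verdict population.** This part needs no historical rate. Take a hypothetical cohort of 10 grade I and 15 grade II/III patients with 6 and 4 successes. The total is 10, so the rule is met. The grade II/III rate is 4/15 = 26.7%, about the historical 26%, yet the conclusion would be drawn for atypical/anaplastic disease.

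**The case against.** The plan contains no arithmetic slip: its alpha, power and stopping probabilities reproduce for the rule and null it names. Section 2.1 looks at the grade I rate and treats its advantage over grade II/III as negligible. A common null follows from that judgement, and the intervals (19.3–32.7% and 20.3–37.7%) overlap almost completely. The expected excess is small: 0.03 × 25 × f is 0.225 successes per cohort at 30% grade I and 0.75 if all are grade I. Uncertainty in the benchmarks matters more. With the interim, a cohort with no grade I patients gives 0.26 if the true grade II/III rate is its upper limit of 32.7%. An all-grade-I cohort gives 0.45 at its upper limit of 37.7% and 0.018 at its lower limit of 20.3%. Both benchmarks come from salvage medical therapy, whereas Cohort 2 also receives radiation, so reweighting them does not make either exact. Finally, Section 2.4 describes the Cohort 1 data to date as grade II or III, so the error-rate point may bear mainly on Cohort 2.

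All of this stands as a limit on the size of the inflation. It does not answer the mismatch in the verdict. Judging the gap negligible may justify pooling, but then the conclusion belongs to the pooled population.

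**Conclusion.** The point holds at moderate severity. Once a cohort includes any grade I patient, the pooled count cannot by itself support a conclusion about atypical/anaplastic meningioma, and the printed 0.089 is no longer that cohort's false-positive rate on the plan's own point estimates. The numerical excess is modest: up to 0.122 (single stage) or 0.112 (with interim) for shares up to one half, and at most 0.160 or 0.148. These figures treat 26% and 29% as known, assume an inactive regimen, and take the grade I share as given.

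A reader might infer that the test is invalid, that the 0.10 limit is certain to be broken, or that the cut-off must become 11. The documents do not support this: they give no grade I share, the cited intervals overlap heavily, and below about 18% (single stage) or 31% (with interim) the limit is kept. Nor should the 0.45 be taken as the size of the problem. It combines an all-grade-I cohort with one end of an interval, and the other end gives 0.018.

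**What to change.** In Section 14.1.4:

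1. Word the verdict for recurrent/progressive grade I–III meningioma, the population of the primary objective.
2. Report PFS-6 with an exact interval for grade II/III and for grade I separately, and make no statement about atypical/anaplastic disease without the grade II/III estimate.
3. State that alpha = 0.089 applies at a 26% null. Beside the 10-of-25 decision, report the exact one-sided p-value against 0.26 × (grade II/III share) + 0.29 × (grade I share), using grade at entry and saying whether the interim is included.

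This takes a few sentences and no extra patients, and grade is already established for eligibility. The cost is a slightly less favourable stated alpha and wide intervals by grade. A cut-off of 11 is optional: it would hold 0.10 at the cited point estimates even in an all-grade-I cohort, but it lowers power at 51% from about 0.88 to 0.80 with the interim.
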